NUMBER	ACTIVE DATE	PAGE
HRP-503	02-04-2020	1 of 35

**Instructions:**

1. Complete **all** sections of the protocol template. By clicking on headers in the Table of Contents below, the form will navigate you directly to that section.
2. If a section does not apply, list Not Applicable as advised.
3. Refer to documents, templates, checklists, SOPs, and worksheets as advised throughout the protocol in **Blue**. Each document referred to in blue contains a hyperlink to the RAP library to obtain the documents (CONTROL + CLICK)
4. Please ensure that your RAP Profile is up to date with your correct email address, phone number, and a current CV/Resume.
5. Upload this completed document into a New Study Submission in RAP (<https://rap.irb.uc.edu/irb>), on the Basic Information Page under “Protocol”.

**TEMPLATE: RESEARCH PROTOCOL**

NUMBER	ACTIVE DATE	PAGE
HRP-503	02-04-2020	3 of 35

STUDY SPECIFIC ABBREVIATIONS/DEFINITIONS:	UCMC is University of Cincinnati Medical Center HH is Holmes Hospital OMS is Oral and Maxillofacial Surgery OR Operating Room ORIF Open Reduction and Internal Fixation AMUPs Anatomic Model Utility Points MVCs motor vehicle collisions CPT The Current Procedural Terminology SSI Surgical site infection VTE Venous thromboembolism
FUNDING SOURCE	N/A
FUNDING LOCATION	 Funds are held in Sponsored Research Services for a Grant or Contract (funds are held internally at UC)  Funds are from a department account (held internally at UC)  Funds held in a corporate account from a Contract (funds held externally from UC)  No funding

**PROTOCOL:**

1.0 OBJECTIVES	1.1 Describe the purpose, specific aims, or objectives.  The goal of treatment is to re-establish the patient's preinjury dental occlusion and facial harmony. Fractures that are nondisplaced and exhibit no occlusal changes may be amenable to nonsurgical management, but most mandible fractures will require stabilization for satisfactory healing and to restore pretraumatic maxillomandibular orientation. Various treatment strategies have been described and vary widely depending on the fracture location and surgeon's preference. The patient's demographics, comorbidities, dentition, and fracture characterization will all influence the choice of fixation by the treating surgeon. [4]
	There are very few randomized control trials that show outcomes when 3D printing is used for intervention planning and performing a procedure. These data are essential to establish value of 3D printing as a clinical service. There is also anecdotal evidence that a 3D printed model of a mandible fracture can be useful for pre-operative planning because the oral and maxillofacial surgeon can better assess the geometry of the bone lesions and can pre-bend fixation plates before the procedure. This hypothetically decreases the amount of time in the operating room.
	The investigators propose a parallel design randomized control trial to study the value of 3D printing for preoperative planning in patients with a fracture of the mandible who require open reduction, internal fixation. The study will be split into two arms: 1) Patients that will

NUMBER	ACTIVE DATE	PAGE
HRP-503	02-04-2020	4 of 35

have a 3D model generated for the surgical procedure 2) The control group who will follow normal standards of care as outlined above and won't have the additional 3D model created pre-operatively.

**1.2 Describe the hypotheses to be tested.**

The investigators will test the hypothesis that patients randomized to the intervention (3D printing with pre-bent plate) arm have less operative room time and less time for the critical part of the procedure than patients in the control arm (no 3D printing, current standards of care). Personalized medicine and care for fracture treatment.

**2.0 BACKGROUND**

**2.1 Describe the relevant prior experience and gaps in the current knowledge.**

Currently, several corporations are contracted with maxillofacial plating companies to provide 3D planning and printing of surgical models, stents, and guides to facilitate surgery. However, these services can be cost prohibitive and can require a considerable lead time. The typical minimum required time of 1 to 2 weeks for the planning and manufacturing process can be limiting when attempting to treat acute injuries in a timely fashion. On-site, or in-house, 3D model fabrication with preoperative plate bending is a cost- and time-effective option to provide predictable reconstructive solutions with an associated decrease in operative time and cost. An inexpensive on-site option mitigates the cost of an outside contracted biomedical engineering service, which has a typical per-case cost of \$1,000 to \$2,000, and decreases the time needed to deliver a patient-specific implant to the OR. [10]

Numerous types of 3D printers are currently commercially available, ranging from industrial machines costing more than \$100,000 to consumer-level products that yield nearly industrial-level results with start-up costs of under \$3,000. [10] The purpose of this study is to evaluate the feasibility, accuracy, and compatibility with current surgical approaches to re-work the current standards of care to include the use of on-site 3D model creation and preoperative plate bending for mandibular fractures.

**2.2 Describe any relevant preliminary data.**

Recent advances in imaging modalities, software technology and 3D printing have allowed for increased accuracy, ability to troubleshoot prior to surgery, and decrease operative time. Virtual surgical planning (VSP) is routinely utilized in maxillofacial surgery for orthognathic surgery, complex craniomaxillofacial trauma, resection and free flap reconstruction of benign and malignant pathology. Typical input is radiographic imaging (CT, CT Angio, MRI, etc.), intraoral scans, 3D facial scans. With the end goal in sight, through virtual surgical planning, cutting guides can be fabricated for accurate osteotomies, intermediate and final dental splints can be created to ensure proper placement of osteotomized segments and custom plates can be fabricated to fixate the bony segments in a predictable fashion.

**2.3 Provide the scientific or scholarly background for, rationale for, and significance of the research based on the existing literature and how it will add to existing knowledge.**

## TEMPLATE: RESEARCH PROTOCOL

NUMBER	ACTIVE DATE	PAGE
HRP-503	02-04-2020	5 of 35

	
3D printing is a technology that allows for physical creation of a 3D model (usually made of plastic) based on computer generated 3D images from CT scans. The 3D images of craniofacial skeleton using computer software are routinely generated and, in turn, these 3D images can be used to create a plastic 3D model using a 3D printer. Unstable or comminuted facial fractures need to be reduced and rigidly fixated using titanium plates and screws. Bending and shaping of the plates is usually performed by free hand based on the surgeon's estimation of what best fits the fracture. Often, bending the titanium plates to the shape of pre-injury skeletal contour is difficult when the bone is fractured into many pieces or is unstable, or when the patient is edentulous (missing several teeth). The process can increase the time spent in surgery and the bent plates may not snugly fit the fracture. For these difficult cases, one option is to use commercially manufactured 3D printed patient-specific models. The patient-specific models provide the benefit of correct shape/form for increased surgical accuracy and decreased intra-operative time. Thus, redefining standards of care increasing surgical satisfaction from the surgeon and patient, while decreasing the time in the OR.

	
3.1 Describe the resources available to conduct the research. Justify the feasibility of recruiting the required number of suitable subjects within the agreed recruitment period, e.g. how many potential subjects do you have access to? What percentage of those potential subjects do you need to recruit?
 
The study will be conducted at University of Cincinnati Medical Center which is designated as the region's only Level I trauma center by the American College of Surgeons. This will be a joint study with the divisions of Oral and Maxillofacial surgery, Plastics and Reconstructive surgery and Otolaryngology who are designated as the primary teams for management of all facial trauma at the institution. Thousands of consults are requested annually through UCMC ED and neighboring hospital systems for these specific injuries.


3.0 RESOURCES AVAILABLE
	
3.2 Describe the time that you will devote to conducting and completing the research, i.e. percent effort.
 
The staff involved with conducting this research project have clinical and didactic responsibilities outside of their research work. The supervisors of this study tend to dedicate one academic day a week for research and other administrative needs, realistically yielding 10-15% of effort on the part of supervisors. However, the main research coordinator and main facilitator of the project has a full-time research position at the division of oral and maxillofacial surgery, where 100% of effort is dedicated towards the research effort.

	
3.3 Describe the availability of medical or psychological resources that subjects might need as a result of an anticipated consequences of the human research.
 
The study will be based out of Holmes Hospital Oral and Maxillofacial Surgery clinic and UCMC. In the event of an emergency (which would be extremely unlikely to be because of the medications used for this study), quick transportation to the emergency department can be arranged. Additionally, a crash cart and complete rescue airway carts are in the clinic,

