**4.1 Detail the investigators' experience as it pertains to the study.**

**4.0 INVESTIGATOR EXPERIENCE**

[name] has been a member of the UC Surgery faculty since 2008. He is currently associate professor of surgery and is serving as the chief of OMS at UC Medical Center and Cincinnati Children's Hospital. [name] obtained his dental degree from Bangalore University, India, and trained in Oral and Maxillofacial Surgery at Emory University's College of Medicine in Atlanta, Georgia. Upon completion of residency, [name] pursued further fellowship training in Oral & Maxillofacial Surgery focusing on orthognathic surgery at Dalhousie University, Halifax, Canada. He currently serves on the Committee of Education and Training (CET) of the AAOMS and is the chair of the special committee on Emerging leaders in OMS. He is also a consultant to the AAOMS Committee on Anesthesia (CAN) on Simulation in Anesthesia. [name] was in the first class of single degree oral and maxillofacial surgeons that were recognized as Fellows of the American College of Surgeons.

[name] is Vice Chair of Operations & Quality at the University of Cincinnati Department of Radiology, and he is the clinical lead for the 3D printing section at UCH. He is the past-Chair of the American College of Radiology Appropriateness Criteria, and the Founding Chair of the Radiological Society of North America 3D Printing Special Interest Group. He also is currently the Editor-in-Chief of the journal 3D Printing in Medicine. [name] obtained his medical

	
degree through the physician scientist program at Harvard -MIT (Medicine and Medical Engineering), and he completed his residency in Diagnostic Radiology at the Brigham and Women's Hospital and Harvard Medical School, Boston, MA.

5.0 STUDY ENDPOINTS	
	
5.1 Describe any primary and secondary study endpoints.
 
Outcome 1: Noninferiority of the clinical outcome (defined by OMS on the post-op, follow up exam approx. 6 weeks out) Based on physical exam
 
Outcome 2:
 
 
Total time in the OR
 
Time in the OR considered critical part of the procedure by the OMS Staff
 
 
Outcome 3
 
 
Subjective outcome to surgeon Likert scale
 
 
5.2 Describe any primary and secondary safety endpoints.
 
Not Applicable.

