**TEMPLATE: RESEARCH PROTOCOL**

NUMBER	ACTIVE DATE	PAGE
HRP-503	02-04-2020	8 of 35

**example, please be sure that what will be done for this research is explained and differentiated from activities that have already taken place or will be submitted for future review. Please note that details about recruitment and consent are asked in later questions.**

The primary goals in the management of mandibular fractures are restoration of functional occlusion and facial form. There are frequently several appropriate techniques available for the definitive management of a given mandible fracture. In general, mandible fractures are treated either closed (maxillomandibular fixation, splinting, modified diet) or open (plates and screws, interosseous wiring, lag screws). The technique chosen depends on several variables including, dental status, fracture characteristics (open, closed, favorable, unfavorable, comminution, bone lose, mechanism of injury, contamination, or frank infection etc.), fracture location, associated injuries, patient mental status and patient desires. The most important considerations are the dental status, fracture characteristics and fracture location.

The main surgical techniques that will be performed will be as follows:

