**6.3 Describe procedures being performed to monitor subjects for safety or minimize risks.**

Several steps are taken to assure patient safety for surgical procedures. Prior to the procedure, their vitals are taken, including their blood pressure, heart rate, respiratory rate, and oxygen saturation. Depending on the patient, especially those with history of cardiopulmonary disease, monitors are kept cycling every five minutes during the procedure. A thorough history and physical is performed before any procedure to assure appropriate patient selection and to rule out more emergent issues. During the procedure, patients are continuously monitored with active physical examinations by the provider. There is always a certified oral and maxillofacial assistant with the patient in the room, especially during the procedure. For urgent-add on, a registered nurse is normally present as well to monitor the patient. The patient is treated via standard protocol of the oral and maxillofacial clinic at Holmes Hospital, which treats thousands of patients annually through safe, effective, and efficient measures. As explained earlier, emergency crash carts, including rescue airway carts, are present at the facility, as well as dozens of trained personnel promptly available if needed.

**6.5 Where applicable, list and describe the data collection tools such as surveys, data collection forms, etc. All tools described should be uploaded in the RAP Smart Form on the Local Site Documents page unless they are standardized, validated tools.**

Data collection will only be stored and collected on REDCap, which is a server software maintained by Cincinnati Children's Hospital Medical Center (CCHMC) informational technology team. The surgeon assigned to the case will fill out the questionnaire outlining the how effective using the 3D model was during the procedure. The outcome data will then be collected on the same secured software.

**6.6 Describe all data that will be accessed and collected during the study and how that data will be obtained (how it will be accessed).**

Description – Distinguish between data accessed and data collected if applicable.

	6.7 If there is a long-term follow-up plan (once all research related procedures are completed), what data will be collected during this period.
	No Long-Term Follow-Up

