**TEMPLATE: RESEARCH PROTOCOL**

NUMBER	ACTIVE DATE	PAGE
HRP-503	02-04-2020	11 of 35

10.0 INCLUSION AND EXCLUSION CRITERIA & VULNERABLE POPULATIONS
	
10.1 Describe how subjects will be screened for eligibility.
 
The screening of potential participants will be performed by the providers of University of Cincinnati Medical Center's Department of Oral and Maxillofacial Surgery clinic located at Holmes Hospital (UCMC OMS HH clinic), or surgical providers from plastic surgery and otolaryngology located in UCMC including resident physicians, attending physicians, research staff, and clinic staff. Surgical team members from the division of plastic and otolaryngology will be consented and recruited to participate in this study by providing their feedback post operatively. The diagnosis and treatment planning will strictly be made by a resident or attending surgeon. However, an elected research coordinator will complete a standardized eligibility form on REDCap based on the study's inclusion/exclusion criteria to finalize participant selection
	
	
10.2 Describe/list the inclusion/exclusion criteria for the study.
 
Inclusion Criteria:
 
Patient ≥ 18 years of age
 
Patients who have received either a cone beam or conventional CT
 
Admitted through UCHMC emergency department
 
All isolated mandible fractures referred to UCH OMS
 
Surgical team members from the division of plastic and otolaryngology
 
Exclusion Criteria:
 
Patient < 18 years of age
 
Patients who have neither cone beam nor conventional CT
 
Patients requiring a repeat procedure
 
Unexpected exposure of hardware
	
	
10.3 Indicate specifically whether you will include each of the following vulnerable populations. Check all that apply. (You may not include members of the below populations as subjects in your research unless you indicate this in your inclusion criteria and are approved by the IRB to include them in your research) The member checklists are for reference only to ensure you provide appropriate safeguards and justification. The checklists do not need to be completed.
	

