**TEMPLATE: RESEARCH PROTOCOL**

NUMBER	ACTIVE DATE	PAGE
HRP-503	02-04-2020	12 of 35

	
of a pregnancy test are negative or until delivery.) (HRP-412 MEMBER CHECKLIST Pregnant Women)
 
 Non-Viable Neonates (HRP-413 – MEMBER CHECKLIST Non-Viable Neonates)
 
 Uncertain Viability Neonates (HRP-414 – MEMBER CHECKLIST Uncertain Viability Neonates)
 
 Prisoners (HRP-415 – MEMBER CHECKLIST Prisoners)
 
10.4 If the research involves individuals listed in 10.3 or other individuals who are vulnerable to coercion or undue influence, please justify based on the applicable checklist and describe additional safeguards included to protect their rights and welfare.
 
N/A
 
10.5 If the research involves or may involve individuals who are students or employees where the research is taking place, please describe additional safeguards included to protect their rights and welfare.
 
Not Applicable

	
11.1 Indicate the total number of subjects to be accrued.
 
We aim to obtain 50 procedures for each arm of the study (100 in total)
 
50: standard surgical procedures aided by use of 3D Printed model
 
50: procedures carried out by standard surgical repair for isolated mandibular fractures (No model)

	
11.2 If applicable, distinguish between the number of subjects who are expected to be enrolled and screened, and the number of subjects needed to complete the research procedures.
 
N/A

	
12.1 Describe when, where, and how potential subjects will be recruited.
 
Subjects of this study are those that require emergent medical attention and are referred to either UCHMS Emergency Department or to UC OMS for treatment. Subjects will be triaged by the clinical providers, and the research coordinator will then complete a standardized informative process. Regardless of involvement, the subject will undergo the same treatment course as any other patient presenting with an isolated mandibular fracture. For the consenting of the surgical team members, they will undergo a research presentation given by the research coordinator in which they have an adequate amount of time to ask any questions or concerns before deciding to be a part of the study.

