
17.0 DATA MANAGEMENT AND CONFIDENTIALITY
	
17.1 Describe the data analysis plan, including any statistical procedures or power analyses.
 
We are going to use the Likert questions to develop a numerical scoring system and report that data as “raw” Likert scores. Likert questions and conversion of specialists’ responses to Anatomic Model Utility Points (AMUPs). Responses of “strongly disagree”, “disagree”, and “neutral” were assigned 0 AMUP points. Responses to preprocedural confidence are assigned negative points, to effectively subtract the impact of the anatomic model post- versus pre-procedure. The maximum AMUP for each patient was 500.

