**TEMPLATE: RESEARCH PROTOCOL**

NUMBER	ACTIVE DATE	PAGE
HRP-503	02-04-2020	18 of 35

	
of REDCap allows for close monitoring of data from the study supervisors. Additionally, only the research coordinator will have capability to add or remove data. REDCap allows the coordinator to designate or prevent specific rights to be assigned from team members.
 
17.4 Describe how data or specimens will be handled study wide as outlined below.
 
17.5 What information will be included in the data or associated with the specimens?
 
No specimens will be collected. The information collected will be as follows:
 
 
Procedural Time
 
Cost differential via model utilization
 
3D Printing Likert scale Questions answered by specialist post operatively
 

--	---

	
17.6 Who will have access to the data or specimens?
 
No specimens will be collected. Data access will be restricted to the research coordinator, the principal investigator, and co-investigators
 
17.7 Where and how data or specimens will be stored?
 
No specimens will be collected. As discussed earlier, all the data will be stored on REDCap.
 
17.8 How long the data or specimens will be stored?
 
No specimens will be collected. The data will be stored for the duration of the study, which is expected to take approximately two years, and for the duration of data analysis and peer-reviewed publication, which is expected to take another year. Realistically, the data will be stored for three years.
 
17.9 If applicable, how data or specimens will be transported?
 
Not Applicable.
 
17.10 Who is responsible for receipt or transmission of the data or specimens?
 
Not Applicable.

--	--

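### No baseline fracture or dental variable is listed for collection, so the operating-room time comparison would be valid but less precise than it need be

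*Protocol*

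**What the plan says.** All references are to the protocol.

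- **Data to be collected.** Section 17.5 opens with "The information collected will be as follows" and names three items: procedural time, cost differential through use of the model, and the specialist's Likert answers. Section 6.6, which should describe the data accessed and collected, still holds the template prompt: "Description – Distinguish between data accessed and data collected if applicable".
- **Case mix.** Section 10.2 takes all isolated mandible fractures, with no limit on site, number or comminution. Section 1.1 narrows this to patients who need open reduction and internal fixation. Section 3.1 adds: "This will be a joint study with the divisions of Oral and Maxillofacial surgery, Plastics and Reconstructive surgery and Otolaryngology".
- **What drives difficulty.** Section 2.3 says that fragmented or unstable bone, or missing teeth, makes plate bending difficult and that this can prolong surgery. On the choice of technique, section 6.2 says: "The most important considerations are the dental status, fracture characteristics and fracture location".
- **Outcome and size.** The hypothesis in section 1.2 concerns operating-room time. Section 5.1 lists total time and "Time in the OR considered critical part of the procedure by the OMS Staff". Section 11.1 plans 50 procedures per arm, 100 in total.
- **Allocation and timing.** Sections 6.1 and 9.2 describe randomisation by the research coordinator after the history and physical, and mention no stratification. Section 10.2 requires imaging before entry: "Patients who have received either a cone beam or conventional CT".

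**The concern.** The protocol names features of the injury that lengthen surgery, admits patients across the full range of those features, and tests a hypothesis about surgical time. It then does not list those features for collection. An analysis plan can choose the model, but it can adjust only for variables that someone has recorded, and it cannot introduce stratification after patients have been allocated. Both have to be settled before enrolment.

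What is at stake is precision. Variation in time that comes from case difficulty stays in the error term unless difficulty is measured and modelled. In a trial of 100 patients that can decide whether a moderate saving in time is detected.

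**Working it through.** **Inputs from the protocol.** 50 per arm (section 11.1); outcome is operating-room time (sections 1.2 and 5.1).

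**Inputs assumed.** The protocol gives no significance level, power, effect size or standard deviation; the analysis text in section 17.1 covers only the Likert scoring. There is thus no sample-size calculation to reproduce. I use two-sided 5%, 80% power and effects in units of the outcome SD. The share of time variance explained by baseline factors, R², is not in the protocol either. I show 10%, 20% and 40%.

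**Step 1: detectable difference without adjustment.** Normal approximation: (1.960 + 0.842) × √(2/50) = 2.802 × 0.200 = 0.560 SD. The two-sample t-test with 98 degrees of freedom gives 0.566 SD. Its power for a true difference of 0.5 SD is 0.697.

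**Step 2: effect of adjustment.** The residual SD becomes SD × √(1 − R²). The detectable difference is therefore 0.566 × √(1 − R²), and power for 0.5 SD is the power of the t-test at 0.5/√(1 − R²). The equivalent unadjusted trial has 100/(1 − R²) patients.

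| R² (assumed) | √(1 − R²) | Detectable difference (SD) | Power for 0.5 SD | Equivalent unadjusted total |
|---|---|---|---|---|
| 0 | 1.000 | 0.566 | 0.697 | 100 |
| 0.1 | 0.949 | 0.537 | 0.742 | 111 |
| 0.2 | 0.894 | 0.506 | 0.790 | 125 |
| 0.4 | 0.775 | 0.438 | 0.892 | 167 |

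The table ignores the few degrees of freedom that the covariates use. That cost is small against 98 but matters most when R² is low, so the covariate list should be short.

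**Step 3: chance imbalance.** Suppose 30% of fractures are complex (assumed). Taking the counts in the two arms as independent Binomial(50, 0.3), the arms differ by at least 5 patients (10 percentage points) with probability 0.326 and by at least 8 patients with probability 0.101. Across assumed prevalences of 10% to 50%, the probability of a gap of at least 5 patients runs from 0.13 to 0.37. If complexity adds 0.5 to 1 SD to operating time (assumed), a 10-point gap moves the observed difference by 0.1 × 0.5 = 0.05 SD to 0.1 × 1 = 0.10 SD. Such movement is already part of the standard error of the unadjusted comparison. Adjustment removes much of it.

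**The case against.** A reader might infer three stronger things, and the protocol supports none of them.

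- **That section 17.5 is a closed list.** It does not say that nothing else will be collected, and it is plainly incomplete: it also leaves out the six-week clinical outcome of section 5.1. Section 6.1 foresees chart review and refers to the patient's condition at surgery, without naming variables. The evidence is of an unfinished description, not of a decision to exclude covariates.
- **That operating-room time will be compared without adjustment.** The protocol states no analysis of time at all, and a separate analysis plan may exist.
- **That imbalance would be uncorrectable or would bias the result.** The CT and chart exist, section 15.1 describes a linking key, and section 17.8 keeps the data through analysis and publication, so the variables could be retrieved. Under randomisation the unadjusted comparison keeps its type I error.

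The number of divisions should not carry weight either. Eligibility in section 10.2 refers to fractures referred to oral and maxillofacial surgery, and section 10.1 recruits plastic surgery and otolaryngology staff to give feedback, while section 23.3 speaks of consented surgeons performing the repair. Which divisions operate is unclear, as is whether the division is known at randomisation. No section says that division affects time, and the sentence quoted from section 6.2 is about technique. Only section 2.3 links case features to longer surgery.

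All of this stands. It limits the point but does not remove it. Retrieval after surgery is a weaker remedy than recording at entry, because later grading can be coloured by operative findings and knowledge of the arm, and section 7.1 deletes the data once the study ends. Retrieval also cannot supply stratified allocation.

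**Conclusion.** The point holds as a gap in planned data collection that costs precision. No baseline fracture or dental variable is named, although the protocol itself says that comminution, instability and edentulism can lengthen surgery. Under the assumed R² of 10% to 40%, recording and adjusting for such factors would be worth about 11 to 67 extra patients in an unadjusted trial of 100. At the low end the gain is modest: 0.57 to 0.54 SD, and power from 70% to 74%. The direction of the gain needs only that the factors named in section 2.3 predict time to a useful degree. Its size rests on R², which the protocol gives no means of estimating. The change should be made because it is cheap; leaving it out does not invalidate the comparison.

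**What to change.** Complete sections 6.6 and 17.5 with fracture site, number of fractures, comminution, and dentate or edentulous status, read from the CT and the history and physical and entered before randomisation. Record the operating surgeon and division as well. Prespecify a linear model for total time and for critical-part time, containing arm and a short list of the pre-randomisation factors.

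Stratifying randomisation by simple versus complex fracture is optional, since adjustment alone recovers most of the precision. Stratifying by division makes sense only if the operating division is known at randomisation; the protocol should say whether it is.

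The cost is a few REDCap fields taken from existing records and, if stratification is chosen, a stratified allocation list. No extra patients, visits or procedures are needed.
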